10.7 Study Duration

The duration of participation for each individual participant is expected to be 2 years (24 months). We plan to recruit and enroll participants starting in April 2015, until June 2015 (over a three month time period). We expect the total duration of the study to last 5 years (60 months) for the completion of all three phases of the study.

10.8 Dissemination

Findings from this research will be disseminated through incorporation into the wellness/benefits design for employees of City of Philadelphia, SEPTA, and IBC. Broader dissemination will include use in benefit design approaches used for IBC throughout the region and more widely through collaborating organizations nationally, other employers, and health delivery organizations once findings are published.

11. Analysis Plan

11.1 Statistical Considerations

Descriptive analyses

We will produce data summaries regularly using frequencies for categorical variables and means, medians, and ranges for continuous variables. We will assess data quality and examine distributional assumptions with graphical methods. To evaluate balance among groups achieved by randomization, we will compare baseline values of all variables across the 4 arms using appropriate tests.

General procedures

All primary analyses will be on an intent-to-treat basis including each participant in the group to which s/he was randomized, regardless of adherence to the assigned strategy. Given the high rates of missing data typical of weight loss studies, handling of missing data is an important issue. Primary analyses will use multiple imputation for the missing in-person weight outcome at 18 months, using the randomization strata (sex, employer, initial BMI), study arm and other baseline variables as predictors in the imputation model. Baseline variables will include age, race, income, education, marital status, household size, physical activities, eating behavior index, stages of change, SF-36 General Health, and baseline weight. Sensitivity analyses will be performed with imputation models that also use post-baseline data, , and recent weight loss trend before drop out, as well as an analysis that assumes that any participants for whom follow-up weight loss data are unavailable have had their weight return to baseline (weight at beginning of Pre Phase). Within each arm, this last assumption is likely to be conservative but this may not be the case in inter-arm comparisons, depending on the dropout rates in

the different arms and true follow-up weights of the dropouts. Thus, a key secondary analysis will consider the effect of differential dropout among the treatment arms. For this analysis, methods that address potential patterns of MNAR may be considered in the missing data imputation, such as pattern mixture models as appropriate. Finally, we will also consider a per-protocol type analysis, which examines the difference in the intervention arms in the complete case data.

Efficacy Analyses

All hypotheses will be tested using two-sided, 0.05-level tests unless otherwise specified (notably the Holm testing approach will be used for the five primary hypotheses in Specific Aims 1-4). The primary analyses will be an unadjusted intent-to-treat analyses, using a t-test for differences in weight change from baseline to 18 months, as measured by the in-person weight, between each intervention group and the control group, and the combined compared to each single intervention, applying the Holm p-value correction for multiple comparisons testing. If weight change appears to be non-normally distributed in the blinded data, we will find an appropriate. Missing data will be handled as described above.

Weight change between baseline and 18 months, with 95% confidence intervals (CIs), will be estimated for comparison with adjusted analyses. We will estimate regression models adjusted for the stratification variables (sex, employer, initial BMI) and other participant characteristics factors including age, race, income, and education. We will evaluate the evidence of confounding for other baseline variables (baseline weight, marital status, household size, physical activities- i.e total minutes of MVPA+walking/week, eating behavior index, stages of change, SF-36 General Health) using change in estimate criterion (10%). We will fit exploratory models of the repeated weight measurements that incorporate time as a polynomial function or using visit-specific indicator variables to determine the most parsimonious model that adequately describes the observed patterns, as necessary. Models will be built separately for the in-person and at home weight data. Models using the at-home weight data would be considered only as potential exploratory analyses comparing the 3 intervention arms, since at-home weights are not available for the control arm. We will investigate random-effects models that allow for baseline individual variability as well as variability in the changes in weights over time; an example is the following: $E(\text{weight}_{ij}) = \beta_0 + \beta_1 \text{Time}_j + \beta_2 \text{Group}_i + \beta_3 X_i + b_{0i} + b_{1i} \text{Time}_j$, where i indicates subject, j indicates assessment times, the parameters are fixed effects linking time, a treatment group vector, and a vector of other demographic or clinical covariates X_i to the outcomes, and b_{0i} and b_{1i} are random intercept and slope effects. Tests for significance of random effects will use likelihood ratio tests for nested models; we will compare models with different random effects structures using the maximized log-likelihoods and the Akaike Information Criterion (AIC). We will apply standard diagnostic techniques to assess model adequacy. We will use treatment by time interactions to assess whether the rate of change in weight differs by intervention arm. We hypothesize that incentives may be more effective among lower income individuals and will evaluate this using interaction terms of income with treatment group. We will explore differential effects by race and education and baseline levels of intrinsic motivation and stages of change. We will also consider other potential mediators, such as the home food and activity environment. To assess the sensitivity of treatment effect estimates to missing

data, we may fit hierarchical or mixed effects models with and without accounting for informative missing data.

For Specific Aim 5, we will consider appropriate methods for cost effective analysis such as the models proposed below. We will assess the costs of each of the intervention arms from both the employer and social perspective and compare the cost differences between each arm relative to the effectiveness measured by incremental weight loss achieved. The principal incremental cost-effectiveness ratios between intervention and control arms will be from the employer's perspective and we will compare costs during the intervention from baseline to 18 months per unit change in weight. Secondary analyses may also 1) evaluate this same ratio but use either 6 months post- intervention data (24 month visit) or 12 months of intervention data (12 month visit) and 2) evaluate these 2 ratios using a limited social perspective. Cost models will use a generalized linear model with a log link and gamma family. Missing data strategies will parallel those described above. We will assess sampling uncertainty for the comparison of costs and effects by calculating parametric 95% CIs for the cost per kg lost and acceptability curves. Standard errors and correlation of the difference in cost and effect will be derived using a bootstrap procedure.

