8.1 Research Design and Methods

Study participants will be obese employees recruited from three employers: SEPTA, IBC, and the City of Philadelphia. We will structure the first 6 months of the study (Phase I) as a weight loss phase in which participants will be encouraged as a weight loss goal to lose 0.5 pound per week [Note: weight loss targets for sample size calculations use kg to fit in with the literature but we will use pounds for the incentive targets, as that is what Americans are most familiar with]. Phase II (months 7-18) will consist of a period of weight loss maintenance in which participants will be able to choose a weight loss goal each month of either 0 or 0.5, pounds of weight loss per week. Phase III (months 19-24) will be a period of post-intervention follow-up concluding with an in-person weigh-in at month 24.

Participants will be randomized to either a control group (information provision and the standard wellness program at each employer along with measurement of weight at 0, 6, 12, 18, and 24 months), a lottery-based financial incentive, or a series of environmental strategies and counseling regarding food intake and physical activity, or a combination of the financial incentive and environmental strategies. Participants in the incentive arm will be eligible for daily winnings based on the weights that are transmitted using wireless scales which we will provide so that they receive daily feedback on their winnings to keep weight loss goals salient. However, we will only provide the full payments based on validation of weight measurement at 6 months intervals, taking advantage of the motivating power of loss aversion by highlighting to participants that they only receive their daily winnings if they continue to

maintain weight loss (or lose further weight) (an approach we have used with great success in previous studies).

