All participants will receive \$50 after validation of weight measurements at months 0, 6, 12, and 24, and \$75 at the 18-month time point, regardless of what their weight is, an approach we have used in many studies to minimize the risk of differential rates of lost to follow-up in the intervention and control arms. The study is powered to test the effectiveness of each intervention arm relative to control as well as the relative effectiveness of the intervention arms. A cost-effectiveness analysis will be conducted to examine potential for wider dissemination and implementation. Measures and time points are shown in Table 1 (attached with the protocol application). We will leverage existing annual biometric assessments done by each of our employer partners at baseline, 12 months, and 24 months for information on glucose, cholesterol, and blood pressure. Dependent measures for primary aims: We will use change in weight as the primary outcome measure. This will match our primary outcome with the tracking that participants are doing on their own at home using wireless scales.

Measures of mechanisms for degree of weight change: Approaches to assessing measures related to daily weight tracking, dietary behavior, physical activity, and psychosocial constructs are as follows: Ongoing tracking of participation: For all participants we will use the Way to Health system to track participation in their respective arm: (1) daily weigh-ins and receipt of incentives (incentive and combined arm); (2) daily weigh-ins and use of environmental strategies at home or at work (environmental, incentive, combined arm); (3) study follow-up visits attended regardless of arm. The Way to Health system will track this using a substantial degree of automation. In the Environmental and Combined arms, use of recommended strategies will be tracked by logs as described above. If necessary, a stepped approach to greater promotion of the strategies will be used to ensure adequate uptake or dose of the environmental strategies

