10.5 Outcome assessments

Weight for all participants will be ascertained in-person upon enrollment into the study and then at the visits at the end of Phase I (6 months), at 12 and 18 months (end of Phase II), and at 24 months (end of Phase III). The primary outcome will be change in the in-person weight from baseline to 18 months. We will utilize other measures collected at months 6, 12, 18 and 24 as part of routine biometric assessments by the participants' employers, all of whom share the same insurance carrier, Independence Blue Cross (IBC). The allowable visit windows for these weight milestones are: -2/+4 weeks for the 6 month visit, -2/+6 weeks for the 12 and 18 month visits, and -2/+8 weeks for the 24 month visit.

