Participants will then receive automated feedback from the system (they may choose text or email) on their progress relative to their goals and their potential earnings, helping to make the payments feel immediate. They will be told that they will receive the full amount if they meet the 6 month target for their weight (the sum of the monthly weight loss goals) but half the money if they do not. Daily monitoring provides participants with a frequent reminder of their goals, chosen because people tend to adopt a narrow frame of reference to diets, rededicating themselves each day. Daily weigh-ins should reduce binge eating by making participants constantly accountable for their weight. Monthly graphical feedback provides encouragement and a symbolic reward for slow and steady progress. Participants in the lottery arm will be eligible for a daily lottery prize with an expected value of \$3.00/day if, prior to resolution of the lottery, they reported a weight at or below their goal on the ideal weight loss trajectory in Figure 4. The lottery provides both infrequent large payoffs (a 1 in 100 chance at a \$100 reward) and frequent small payoffs (a 1 in 5 chance at a \$10 reward) since subjects are motivated by both the future (fixation on large potential winnings) and the past (how often did I win?). Subjects will be assigned a 2-digit number with two distinct digits upon entry into the study, e.g. 27. A two digit random number will be generated for each day. If the last digit includes either a 2 or 7 (a 1 in 5 chance), and the subject reported a weight at or below target weight, s/he wins \$10. If the two digits are 27 (a 1 in 100 chance) the subject wins an additional \$100. When a subject reports a weight above target, we will still generate a 2-digit daily number and tell the subject if s/he would have won the lottery that day if s/he had reported a weight at or below target. We believe that a desire to avoid the regret associated with not winning combined with learning that one would have won, had one been adherent, will motivate participants to a greater degree than only on the value of the rewards. A key aspect of the weight loss trajectory is that it can be reset monthly, a critical feature in the likely event that a participant falls short of attaining a monthly weight loss goal. To avoid discouraging such subjects, who would otherwise suddenly have to lose a lot of weight to get back on track and might decide to drop out of the study, each participant will be given the opportunity for a fresh start. The overall goals set at beginning of Phase I will stay the same, but the slope of the trajectory will adjust (i.e., steepen) such that the participant need not binge diet following a month of poor weight loss performance (see Fresh start trajectory in Figure 3, for a subject who lost 1 lb. instead of 4 lbs. in first month). Keeping the overall weight loss goal constant makes the procedure fair for participants who maintain the ideal trajectory, while adjusting the slope of the weight loss line allows for recovery from slip-ups, an approach we have used to attain minimal lost to follow-up rates of less than 10% in previous weight loss studies. To give participants frequent feedback, we will pay out 50% of winnings to date at the end of each month. To minimize falsification of weights and to utilize the amplification of motivation provided by loss aversion, the other half will be held in a virtual account and paid to participants at the end of each 6-month

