
period only if they have met or exceeded their monthly goal. The monthly goal will include a two-pound margin to account for the added weight of clothing worn by participants at each 6 month in-person weigh-in. Between months 19-24 (Phase III), participants will not receive incentives tied to weight maintenance to evaluate sustainability of effects achieved in Phases I and II.

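### The primary imputation of 18-month weight leaves out the in-person 6- and 12-month weights that every arm provides, which costs precision and can bias arm contrasts

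*Combined protocol and SAP*

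**What the plan says.** Section 11.1 (General procedures) makes multiple imputation of the missing 18-month in-person weight part of the primary analysis. The predictors are sex, employer and initial BMI, then "study arm and other baseline variables as predictors in the imputation model". The baseline variables are listed by name, and no follow-up weight is among them.

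Follow-up data come in one level down: "Sensitivity analyses will be performed with imputation models that also use post-baseline data", together with the weight trend before dropout. A return-to-baseline analysis is also planned. The section goes on: "Thus, a key secondary analysis will consider the effect of differential dropout among the treatment arms", for which pattern-mixture or similar methods may be considered. Repeated-measures models appear under Efficacy Analyses, but as exploratory or optional work.

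Sections 8.1 and 10.5 have all participants, controls included, weighed in person at 6 and 12 months as well as at baseline, 18 and 24 months. The plan gives no reason for keeping those two weights out of the primary imputation.

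**The concern.** A baseline-only model fills in a missing 18-month weight as if the person were an average member of the arm with those baseline characteristics. That is right only if, given arm and baseline, leaving is unrelated to how the person has done so far. Two features of the plan make this doubtful, although neither shows that it will fail.

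- Section 10.6, on participants who fall behind: "might decide to drop out of the study, each participant will be given the opportunity for a fresh start". The fresh start is there to prevent a link between poor progress and dropout that the authors consider plausible.
- In the lottery and combined arms, section 8.1 says "we will only provide the full payments based on validation of weight measurement at 6 months intervals". Section 10.6 holds back half the winnings and pays it at the end of each six-month "period only if they have met or exceeded their monthly goal". Participants in these two arms therefore have a reason to attend that depends on their weight; those in the other two arms do not.

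The held-back payment differs between the two arms in three of the five primary contrasts (lottery vs control, combined vs control, combined vs environmental). It is common to both arms in environmental vs control and combined vs lottery.

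At stake are the five Holm-tested primary comparisons, all of which rest on the baseline-only imputation. The 3 kg contrasts of Aim 4 have the least room. The plan does not say what to conclude if the sensitivity imputation disagrees, and changing models after unblinding would look post hoc.

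**Working it through.** **Inputs from the plan.** SD of weight change 5 kg and 20% missing at 18 months (section 5.2); original target 328, so 328/4 = 82 per arm, with 260 (65 per arm) expected at 18 months; two-sided 0.05 with Holm over five comparisons; stated power 87% for 3 kg (sections 11.1 and 11.2).

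**Reproducing the plan's figure.** The standard error of a contrast is 5 × √(2/65) = 0.877 kg. Under the planned effects the three control comparisons have over 99% power and reject first, so the two 3 kg tests start at 0.05/2 = 0.025. Power for 3 kg there is 87.4% (t) or 88.1% (normal), which matches 87%.

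**Size of the held-back payment.** Expected winnings are 0.2 × $10 + 0.01 × $100 = $3.00 a day. Half of that over six months is $3.00 × 182.6 / 2 = $274 for someone on target every day. The visit payment made regardless of weight is $50 or $75.

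**Assumptions not in the plan.** Correlations of weight change of 0.80 (6 with 12 months), 0.85 (12 with 18) and 0.68 (6 with 18); dropout odds ratio 1.11 to 1.35 per kg less lost; baseline variables only weakly predictive of weight change.

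**Bias with baseline-only imputation** (large-sample simulation, true difference 5 kg, dropout depending on 12-month change):

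| Dropout pattern | 20% missing | 10% missing |
|---|---|---|
| Weight-linked in one arm only | 0.4 to 1.0 kg | 0.2 to 0.5 kg |
| Half the slope in the other arm | 0.2 to 0.4 kg | 0.1 to 0.2 kg |
| Equal slopes, 15% vs 25% missing | 0.2 to 0.45 kg | – |
| Same slope and rate in both arms | 0 | 0 |

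Swapping the arms reverses the sign. As a plausibility check, the bias in an arm is roughly the missing fraction times the gap in mean 18-month change between completers and dropouts. At 20% missing, 0.4 to 1.0 kg implies a gap of 0.4/0.2 = 2 kg to 1.0/0.2 = 5 kg. A different set of assumptions (a single odds ratio of 1.22 per kg, correlations 0.7 to 0.9) gave 0.57 to 0.76 kg for the one-arm case and 0.27 to 0.36 kg for unequal rates.

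**Bias with the 6- and 12-month weights added** (one-arm case, 20% missing):

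- Dropouts have both weights: about 0.
- Dropouts have only the 6-month weight, or a third each have both, one or none: 0.2 to 0.4 kg remains.
- Attendance depends on the 18-month weight itself, interim weights complete: bias falls from 0.5–1.1 kg to 0.1–0.4 kg (0.2–0.65 kg if the correlations are 0.70).

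**False-positive rate.** Multiple imputation with 82 per arm, 20 imputations, odds ratio 1.22, no true difference, nominal two-sided 0.05: 13% (one arm only), 6% (half slope) and 4% (identical dropout), against 4 to 5% with interim weights.

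**Precision when dropout is unrelated to weight.** Let ρ be the correlation of interim with 18-month change and f the share of dropouts who have an interim weight. The variance ratio is (1 − ρ²) + ρ² × 65/(65 + 17f).

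- ρ = 0.6, f = 0.3: 0.64 + 0.36 × 65/70.1 = 0.974; SE 0.865 kg.
- ρ = 0.9, f = 1: 0.19 + 0.81 × 65/82 = 0.832; SE 0.800 kg.
- Over this range, power for 3 kg at 0.025 rises from 88.1% to between 89.0% and 93.4%. If f = 0 there is no gain.

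Under the correlations assumed above and complete interim weights, the simulated SE is 0.88 vs 0.81 kg. Power for 3 kg is then 92% vs 96% at 0.05, 87% vs 92% at 0.025, and 78% vs 86% at 0.01 (78–79% vs 82–83% at 0.01 if dropouts have both, one or no interim weight in thirds).

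**The case against.** The strongest objection is that the held-back payment turns on weight at the visit itself. Participants in these arms weigh themselves daily, so they know where they stand before the 18-month weigh-in. Attendance would then depend on the missing value, and interim weights only partly help. If, in addition, only a third of dropouts have both interim weights, a third one and a third none, the one-arm bias falls only from 0.50–1.14 kg to 0.31–0.73 kg. This stands. It is a reason to keep the planned differential-dropout and missing-not-at-random analyses, not a reason to prefer the baseline-only model, which does worse in the same setting.

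Second, the plan already specifies the better imputation as a sensitivity analysis, so the dispute is about which model is primary. That is true, but the confirmatory tests use the primary one.

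Third, the inputs are soft and the gain modest. The correlations, the dropout slopes and the share of dropouts with interim weights are all assumed. At the relevant Holm step the power gain is about 1 to 5 points, and planned comparisons with control keep over 99% power either way. Section 10.6 cites losses below 10% in previous studies, and section 8.1 pays for attendance regardless of weight "to minimize the risk of differential rates of lost to follow-up in the intervention and control arms". The $274 applies only to someone always on target. The per-arm figure of 82 is the original target; the current one is 344/4 = 86, which would give 5 × √(2/(0.8 × 86)) = 0.85 kg. All of this limits the size. None of it favours ignoring the interim weights.

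**Conclusion.** The concern holds. The plan collects the best available predictors of a missing 18-month weight in every arm and leaves them out of its primary imputation without giving a reason. The loss of precision is fairly sure but small, and it matters mainly for the 3 kg contrasts. The bias is conditional: it needs dropout to depend on interim weight and to differ between arms in strength or rate, and it can go either way. Under the stated assumptions it could reach about one planned standard error in the one-arm case, and about a quarter to a half of one in the milder cases at 20% missing. The reading of the plan is firm; the size rests on correlations and dropout slopes that the documents do not give. This should be fixed before the analysis, but it is not a fatal flaw.

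**What to change.** In section 11.1, exchange the roles of two imputations that are already planned:

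- **Primary:** impute 18-month weight from the in-person 6- and 12-month weights (themselves imputed in sequence when missing), the strata and the listed baseline variables, separately by arm or with arm interactions.
- **Sensitivity:** the baseline-only model.
- **Exclude from the primary model:** home-scale weights, because the control arm has none.
- **Keep:** the return-to-baseline, differential-dropout and missing-not-at-random analyses. The change reduces but does not remove bias for people who leave before an interim weight or whose attendance depends on the 18-month weight.

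The cost is a change of SAP wording and a few lines of imputation code, with no new data. The downside is a slightly more complex, sequential imputation model.
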